5.3.4. Compliance

Subject compliance (defined as having taken 80% to 120% of study medication) will be assessed at each clinic visit (except Day 1) by counting the tablets remaining since last dispensing. Subjects who are non-compliant will be counseled on the importance of complying with study requirements.

Subsequently, if by investigator assessment the subject is not at least 80% compliant with study medication or other protocol specified requirements, the subject will not be considered as having completed all protocol requirements. Investigators should indicate on the appropriate CRF page non-compliance with study treatment.

Inventory control of all study medications must be rigorously maintained throughout the duration of the study until all medication has been accounted for and/or returned to the sponsor. Any discrepancies noted between Drug Dispensing Records and the drug inventory must be reported to Pfizer.

5.4. Drug Storage and Drug Accountability

Drug should be stored in accordance with the drug label. It is to be stored at controlled room temperature 15°C-30°C (59°F-86°F). (For Malaysia room temperature is defined as 15°C-25°C (59°F-77°F).

Storage conditions stated in the Single Reference Safety Document (SRSD) (*Investigator Brochure (IB)*), will be superseded by the label storage.

The investigator, or designee (eg, pharmacist), will ensure that all study drugs are stored in a secured area, under recommended storage condition and in accordance with applicable regulatory requirements. Investigators and site staff are reminded to check temperatures (ie, manually or by using alarm systems to alert of any excursions) and ensure that thermometers are working correctly as required for proper storage of the investigational products. Temperature monitoring procedures and equipment should include the monitoring of minimum and maximum temperatures for awareness of potential temperature excursions at times when site staff are not actively monitoring/recording temperatures. Deviations from the storage requirements, including any actions taken, must be documented and reported to the sponsor. Once a deviation is identified, the investigational product must be quarantined and not used until the sponsor provides documentation of permission to use the investigational product.

The investigator must ensure that authorized personnel correctly receive deliveries of investigational product from the sponsor and that all receipts are recorded in writing. Drug shipments must be recorded as “received” in the automated tele-randomization system. All drug shipment confirmation notices from the automated tele-randomization system must be retained in the site study files.

To ensure adequate records, all study drugs dispensed to subjects will be accounted for on drug accountability inventory forms completed as instructed by Pfizer. Documentation will include date of receipt and amounts dispensed to and returned by study subjects. All blisters (including empty blisters packs) must be returned to the investigator by the subject.

At the end of the trial, Pfizer will provide instructions as to disposition of any unused investigational product. If Pfizer authorizes destruction at the trial site, the investigator must ensure that the materials are destroyed in compliance with applicable environmental regulations, institutional policy, and any special instructions provided by Pfizer. Destruction must be adequately documented. Unless otherwise authorized by Pfizer, at the end of the clinical trial all drug supplies unallocated or unused by the subjects must be returned to Pfizer or its appointed agent (eg, Contract Research Organization (CRO)).

5.5. Concomitant Medication(s)

Concomitant medications should remain stable throughout the treatment phase of the study, where possible. Changes in concomitant medications can and should be made where issues of subject safety are evident. Current country label or Investigator’s Brochure should be consulted to determine other medications that cannot be administered with sildenafil citrate.

Prohibited During Study

- Bosentan is not permitted. Subjects who receive bosentan will be discontinued from study treatment and followed for survival for the duration of the study;
- Riociguat is not permitted. Subjects who receive riociguat will be discontinued from study treatment and followed for survival for the duration of the study;

- Any agent that is a potent CYP3A inducer or inhibitor (Appendix 1) that has the potential for any clinically evident drug-drug interaction with sildenafil;
- Concomitant therapy with any PDE-5 inhibitor; and
- Nitrates or nitric oxide. Sildenafil was shown to potentiate the hypotensive effects of nitrates, and its administration to patients who are using organic nitrates, either regularly and/or intermittently, in any form is contraindicated.

Permitted During Study

- Background treatment with endothelin receptor antagonists (ETRA) other than bosentan (ie, ambrisentan and any other ETRA that becomes available during the conduct of the study provided that the new agent is not a potent CYP3A inducer or inhibitor that has any clinically evident drug-drug interaction with sildenafil) and/or prostanoids will be permitted and is to be continued during the study.
- Add-on treatment specific for PAH with drug classes other than PDE-5 inhibitors (ie, ETAs as described above, oral, inhaled or SC prostanoids, or IV epoprostenol) will be permitted as needed for clinical worsening during the trial.
- Any other novel agents that are approved for use in adult PAH that become available during the course of the study will be permitted as long as there are no clinically evident drug-drug interactions and are in the opinion of the investigator safe when co-administered with sildenafil.
- Supportive non-PAH-specific treatment (eg, oxygen, digoxin, diuretics and inotropes) will be permitted at any time during the study.
- Warfarin (and other vitamin K antagonists), angiotensin-converting enzyme (ACE) inhibitors, angiotensin-2 receptor blockers (ARB), calcium channel blockers will be permitted during the study.
- Medications for other concurrent illnesses necessary for the subject's well-being are permitted at the discretion of the investigator.

All concomitant medications (including changes in doses) should be entered in the appropriate CRF page.

Prior Medications

Prohibited Prior Medications

- Subjects who had prior long term treatment with PDE-5 inhibitors will be not be eligible to participate in the study

- Subjects should not have had a change in dose or class of standard background therapy used for treatment of PAH (eg, oxygen, calcium channel blockers, digoxin, diuretics) within 30 days prior to randomization. Exception is established treatment with anticoagulants where a subject's dose may need to be adjusted based on INR and changes in flow rate of oxygen.
- All prior medications taken for the treatment of PAH should be entered in the appropriate CRF page.

6. STUDY PROCEDURES

6.1. Screening (up to 21 days prior to Day-1)

- The following will be done:
- Inclusion and exclusion criteria;
- Demographic details (including ethnicity, race, weight, height, smoking and alcohol usage);
- Primary diagnosis;
- Medical history including drug allergies;
- Complete physical examination;
- WHO Functional Class;
- Lung function tests to determine total lung capacity (TLC) and forced expiratory volume (FEV₁) in subjects with a history of scleroderma, COPD or other chronic or restrictive lung disease (if not performed within the last 12 months);
- Vital signs: blood pressure and pulse rate after sitting for 5 minutes;
- 12-Lead electrocardiogram (any time within the Screening window up to Day 1):
- Chest X-Ray (PA; obtained at Screening or prior to Day 1 unless performed and results available within previous 12 months);
- Blood sample for biochemistry and hematology (safety laboratory tests);
- Quantitative serum pregnancy test for women of childbearing potential;
- In women of childbearing potential, documentation in the source documents of assignment of a highly effective method of contraception that will be used for the length of the study;
- 6MWT;

- BORG dyspnea score;
- Collection of prior and concomitant treatment(s); and
- Informed consent.

6.2. Day 1 (up to 21 days after screening visit)

The following will be done:

- Review inclusion and exclusion criteria to confirm eligibility;
- Brief physical examination;
- Vital signs: blood pressure and pulse rate after sitting for 5 minutes;
- A qualitative urine pregnancy test (sensitivity of at least 25 mIU/mL) for women of childbearing potential will be obtained at the study site (if result is indeterminate or positive, a serum sample should be collected for quantitative pregnancy test and assayed by the central laboratory and study drug should not be dispensed). **Result must be negative prior to dispensation of study medication;**
- For women of childbearing potential, confirm that a highly effective method of contraception is being used;
- 6MWT;
- BORG dyspnea score;
- Assessment of survival and clinical worsening;
- Collection of adverse events;
- Collection of concomitant treatment(s);
- Randomization (IVRS/IWRS);
- Dispense study drug (2-week supply);
- 1st dose of study drug, subject instruction on dosing, storage; and
- Dispense diary.

6.3. Week 2 (± 3 days of Day 1 visit)

The following will be done:

- Brief physical examination;

- Vital signs: blood pressure and pulse rate after sitting for 5 minutes;
- For women of childbearing potential, confirm that a highly effective method of contraception is being used;
- Assessment of survival and clinical worsening;
- Collection of adverse event(s);
- Collection of concomitant treatment(s);
- Collect and review returned study medication blister packs;
- Collect and review subject diary for dosing and adverse events;
- Complete dosing log and calculate compliance;
- Dispense new cartons of study medication; and
- Dispense new subject diary.

6.4. Months 3 and 9 (Visit window \pm 10 days)

The following will be done:

- Brief physical examination;
- WHO Functional Class;
- Vital signs: blood pressure and pulse rate after sitting for 5 minutes;
- Blood sample for biochemistry and hematology (safety laboratory tests);
- For women of childbearing potential, confirm that a highly effective method of contraception is being used;
- Assessment of clinical worsening and survival;
- Collection of adverse event(s);
- Collection of concomitant treatment(s);
- Collect and review returned study medication blister packs;
- Collect and review subject diary for dosing and adverse events;
- Complete dosing log and calculate compliance;

- Dispense new cartons of study medication;
- Dispense new subject diary.

6.5. Months 6, 12, 18, 24, 30, 36, 42, 48, 54, 60, 66, 72, 78, 84, 90 and 96 (followed by every 6 months until end of study treatment; Visit window \pm 10 days)

The following will be done:

- Physical examination (Complete exam will be performed annually at months 12, 24, 36, 48, 60, 72, 84 and 96 until the end of the study treatment; a brief exam will be performed at the other visits);
- WHO Functional Class;
- Vital signs: sitting blood pressure and pulse rate after sitting for 5 minutes;
- Blood sample for biochemistry and hematology (safety laboratory tests);
- For women of childbearing potential, confirm that a highly effective method of contraception is being used;
- 6MWT performed close to trough levels of sildenafil (ie, at least 4 hours after the last scheduled dose);
- BORG dyspnea score;
- Assessment of survival and clinical worsening;
- Collection of adverse event(s);
- Collection of concomitant treatment(s);
- Collect and review returned study medication cartons;
- Collect and review subject diary for dosing and adverse events;
- Complete dosing log and calculate compliance;
- Dispense new cartons of study medication;
- Dispense new subject diary.

6.6. Months 15, 21, 27, 33, 39, 45, 51, 57, 63, 69, 75, 81, 87, 93, 99 (followed by every 6 months until end of study treatment; Visit window \pm 10 days)

The following will be done:

- Collection of adverse event(s);
- Collect and review returned study medication cartons;
- Collect and review subject diary for dosing and adverse events;
- Complete dosing log and calculate compliance;
- Dispense new cartons of study medication;
- Dispense new subject diary.

If it is impossible for subjects to come to the study site for visits on these months ONLY, alternate arrangements can be made. Information can be collected by telephone and drug can be shipped from the site to the subject by courier (with required signature) or dispensed to a subject designated person according to local regulations. This process must be documented in the source documentation and Sponsor must be notified.

6.7. End of Treatment Visit (Visit window \pm 7 days)

The following will be done:

- Complete physical examination;
- WHO Functional Class;
- Vital signs: sitting blood pressure and pulse rate after sitting for 5 minutes;
- Blood sample for biochemistry and hematology (safety laboratory tests);
- A qualitative urine pregnancy test (sensitivity of at least 25 mIU/mL) for women of childbearing potential will be obtained at the study site (if result is indeterminate or positive a serum sample should be collected for quantitative pregnancy test and assayed by the central laboratory and study drug should not be dispensed);
- For women of childbearing potential, confirm that a highly effective method of contraception is being used and will continue for at least 28 days after discontinuation of study treatment;
- 6MWT (performed close to trough levels of sildenafil (ie, at least 4 hours after the last scheduled dose);
- BORG dyspnea score;

- Assessment of survival and clinical worsening;
- Collection of adverse event(s);
- Collection of concomitant treatment(s);
- Collect and review returned study medication cartons;
- Collect and review subject diary for dosing and adverse events;
- Complete dosing log and calculate compliance.

6.8. Follow-up Check (28 days \pm 7 days)

Collection of adverse event(s).

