6.9. Study Treatment Withdrawal

Subjects who discontinue randomized study treatment for any reason will continue to be followed for survival at the time points specified in the schedule of activities for the duration of the study. All efforts should be made to follow all subjects for these data through standard of care visits or phone contact regardless of their participation in required study assessments (ie, 6MWT).

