8.2. Reporting Period

For SAEs, the active reporting period to Pfizer or its designated representative begins from the time that the subject provides informed consent, which is obtained prior to the subject's participation in the study, ie, prior to undergoing any study-related procedure and/or receiving investigational product, through and including 28 calendar days after the last administration of the investigational product. Serious adverse events occurring to a subject after the active reporting period has ended should be reported to the Sponsor if the investigator becomes aware of them; at a minimum, all serious adverse events that the investigator believes have at least a reasonable possibility of being related to study drug are to be reported to the Sponsor.

AEs (serious and non-serious) should be recorded on the case report form (CRF) from the time the subject has taken at least one dose of study treatment through the last subject visit.

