The sites with subjects who do not have post-study PAH treatment options currently available received a second Investigator's letter, on 30 July 2020. For those subjects, sites were instructed to schedule a regular Study Visit before 15 August 2020 to ensure that all subjects receiving sildenafil 5 mg (TID) discontinue their treatment as soon as possible and continue on 20 mg (TID) (the currently approved dose). This needs to be accomplished in a blinded fashion at the scheduled visit as follows:

- Subjects must be informed about the DMC recommendation and their consent to continue in the study obtained.
- Subjects must be informed that if they agreed to continue participation in the study and are currently receiving 5 mg (TID), their dose would be automatically increased to 20 mg (TID); for subjects currently receiving either 20 mg sildenafil (TID) or 80 mg sildenafil (TID), the dose would remain unchanged. Both the investigator and the subject will remain blinded to the study treatment.
- A new blinded study drug kit will be assigned and dispensed to all subjects.

The IVRS/IWRS system will be set to close the sildenafil 5 mg (TID) treatment arm and to replace it with sildenafil 20 mg (TID). This will ensure that all subjects in the 5 mg TID arm will be increased to 20 mg TID in a blinded manner, as follows:

1. Subjects on 5 mg TID will be increased to 20 mg TID and will continue in the study on 20 mg TID until the End of Treatment Visit.
2. For subjects on 20 mg TID or 80 mg TID, the dose will remain unchanged until the End of Treatment Visit.

To ensure continuity of study treatment with sildenafil, subjects are allowed to stay in the study until they can be enrolled into a program that will provide access to prescription sildenafil at the time of the End of Treatment Visit.

After completing the End of Treatment Visit, a 28-day follow-up visit will be scheduled at which time the End of Study CRF page will be completed. This will conclude the subject's participation in the trial.

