5. ANALYSIS SETS

5.1. Full Analysis Set

The intent-to-treat population (ITT) will consist of all randomized patients treated with study treatment. The primary efficacy analysis will be conducted using ITT population.

5.2. 'Per Protocol' Analysis Set

The Per-protocol population (PP) will consist of randomized subjects who receive at least 1 dose of study treatment and contribute at least 1 post-baseline visit. The time to event endpoint for this PP will consist of all events that occur while the subjects are on study treatment without major protocol deviations/violations through 35 days after the last dose of the study treatment, since randomization. This collection period (from randomization to

35 days after the last dose of the study treatment) will also be applied to other efficacy endpoints with PP analyses.

The efficacy analyses of primary and secondary endpoints will be conducted using the per-protocol (PP) population as sensitivity analyses.

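### The follow-up check may be made up to 7 days before the 28-day SAE period ends, and no later visit asks about adverse events

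*Protocol*

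**What the plan says.** Protocol 6.8 is headed "6.8. Follow-up Check (28 days \pm 7 days" and lists one task: "Collection of adverse event(s". It does not name the date from which the 28 days are counted. The main Schedule of Activities and the separate Schedule for subjects who stop study treatment both show this check with a ±7-day window, and adverse events are the only item marked for it.

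Protocol 8.2 sets three rules:

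- The active SAE period runs "through and including 28 calendar days after the last administration of the investigational product".
- SAEs after that period "should be reported to the Sponsor if the investigator becomes aware of them".
- Adverse events, serious or not, go on the case report form "from the time the subject has taken at least one dose of study treatment through the last subject visit".

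After treatment stops, Protocol 6.9 says subjects "will continue to be followed for survival at the time points specified in the schedule of activities for the duration of the study". In the Schedule for those subjects, the 3-monthly contacts are marked for survival only.

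For subjects kept on treatment under Appendix 6, "a 28-day follow-up visit will be scheduled at which time the End of Study CRF page will be completed", and that visit closes their participation. SAP 6.1 censors subjects who complete the study at their last visit.

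SAP 5.2 uses a different limit for per-protocol events: "through 35 days after the last dose of the study treatment, since randomization".

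**The concern.** Two windows that should fit together do not. The SAE period has a fixed end at Day 28. The contact that should ask about that period may take place a week before it ends, and a site that does so has broken no rule. Protocol 8.13 expects each subject to be questioned about adverse events, which needs a contact, and none is scheduled after this one.

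What is at stake is even and complete post-treatment safety data. The SAP 6.2 definition of a treatment-emergent event has no cut-off after treatment, and SAP 8.4 computes incidence over all treated subjects. For a subject whose check is the last visit, the end of recording on the case report form is the check date, so observation depends on when the site made the call. An SAE on Day 25 after a final visit on Day 21 would be reportable to the sponsor under one sentence of 8.2 but outside the recording period in another.

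**Working it through.** The plan gives no figure of its own on this point, so the check is calendar arithmetic plus a rough scale for deaths.

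**Inputs**

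- Check: target 28 days, tolerance 7 days (Protocol 6.8, both Schedule tables).
- End of active SAE period: Day 28 after last dose, inclusive (Protocol 8.2).
- Adverse-event contacts after the check: none (both Schedule tables).
- Design mortality 15% at 2 years, 429 subjects, 143 per arm, 143 deaths required (Protocol 9.1).

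**1. Permitted days.** Earliest 28 − 7 = Day 21. Latest 28 + 7 = Day 35.

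**2. Days of the SAE period left after the check**, if it is timed from the last dose: max(0, 28 − check day).

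- Day 21: 28 − 21 = 7 days.
- Day 27: 28 − 27 = 1 day.
- Day 28 or later: 0 days.

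**3. Effect of the missing anchor.** Suppose the 28 days run from an End of Treatment visit held k days after the last dose. The check then falls on Days 21 + k to 35 + k, and the largest gap is 28 − (21 + k) = 7 − k. The documents do not give k. Taking 0 to 7 days as an assumption:

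- k = 0: Days 21-35, gap up to 7 days.
- k = 7: Days 28-42, no gap.

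Over the whole range the check can fall on Days 21-42, and Day 21 remains the earliest.

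**4. What can still find an event after an early check**

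- Non-fatal SAE to Day 28: the reporting duty in 8.2 holds, but no contact prompts it.
- Death in a subject who stopped treatment early: found at the 3-monthly survival contacts.
- Death in a subject whose check is the last contact: no scheduled contact.

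**5. Scale for deaths.** With a constant hazard, h = −ln(1 − 0.15)/2 = 0.0813 per year.

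- 7 days: 1 − exp(−0.0813 × 7/365.25) = 0.00156; × 429 = 0.67 deaths. In the two arms of the primary comparison, 2 × 143 = 286 subjects, 0.45.
- 14 days (Days 22-35, to the end of the SAP 5.2 window): 1 − exp(−0.0813 × 14/365.25) = 0.00311; × 429 = 1.33 deaths. In 286 subjects, 0.89.

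These figures suppose that every subject is checked on Day 21 and has no later contact, which overstates the numbers exposed. They use the design's average hazard; the hazard just after stopping treatment could differ, and the documents do not quantify it.

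**6. After the fix.** With Days 28-35 counted from the last dose, the largest gap is max(0, 28 − 28) = 0 days.

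**The case against.** The strongest reply is that nothing is lost by rule. Protocol 8.2 sets the SAE duty by calendar, whatever the date of the check. Later SAEs are still reportable on awareness, and 8.14.1 requires notification within 24 hours of awareness. A symmetric ±7-day window around a Day 28 target is ordinary practice, and many checks will fall on or after Day 28. All of this stands. A reader might infer that late post-treatment events go uncollected; the documents do not support that. The gap is in active questioning, and only when the check is early.

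A reader might also infer that two weeks of the 35-day per-protocol window are unobserved. That does not follow either:

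- The SAP 5.2 window governs efficacy events, while the check collects adverse events.
- Deaths in subjects who stop treatment early are picked up by the 3-monthly survival contacts.
- Clinical worsening is scheduled for assessment only up to the End of Treatment visit (Protocol 7.3 and the Schedule), so the lack of later assessment does not come from the check's window.
- What remains is mortality in subjects whose check is their last contact, such as those under Appendix 6. The documents do not give the size of that group.

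Finally, it is tempting to spread the checks evenly over the window and quote a share made early. The documents give neither the distribution of check days nor the anchor, so no such percentage is warranted.

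**Conclusion.** The point holds as a mismatch between Protocol 6.8 and 8.2. A compliant check can precede the end of the active SAE period by up to 7 of its 28 days, and no later scheduled visit asks about adverse events. The 7 days assume timing from the last dose; they shrink to 7 − k if the anchor is an End of Treatment visit k days later.

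The consequence is modest: uneven active questioning in the last week of the SAE period. With sites blinded, there is no stated reason for early checks to favour one arm.

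The effect on the primary intent-to-treat mortality analysis is negligible. Subjects who stop early stay in survival follow-up. Even with all 429 subjects exposed to the gap, the expected number is 0.67 deaths in 7 days, or 1.33 in 14, against 143 required. Per-protocol is a sensitivity analysis only. This is a low-cost improvement in safety data collection and does not threaten the trial's conclusion.

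**What to change.** In Protocol 6.8 and both Schedule tables, count the check from the last dose and allow it only on Days 28-35 (28 days, +7/−0). Add survival status to what is recorded at that contact: under Appendix 6 it ends participation, and completers are censored at their last visit.

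The change needs wording in three places and one added item on an existing contact; it adds no visit. The cost is that sites lose the 7 days of scheduling room before Day 28.

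Leave the 35-day window in SAP 5.2 unchanged. Shortening it to 28 days would discard deaths on Days 29-35 that survival follow-up does capture, and would alter a sensitivity analysis after the unblinded interim analysis.

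New wording cannot recover checks already made at close-out. For those, a table of the actual check day relative to the last dose would show how many were early.
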